# The Early Feasibility Study of the Intrepid™ TMVR Transseptal System Clinical Investigation Plan

Version 4.0

Page 29 of 102

Medtronic

17. Hemodynamic instability requiring dependency of either inotropic agents or mechanical circulatory support
18. Subject refuses a blood transfusion
19. Subject unwilling or unable to adhere to the protocol specified anticoagulation treatment
20. Blood dyscrasias as defined: leukopenia (WBC <1000 cells/mm^3), thrombocytopenia (platelet count <50,000 cells/mm^3)
21. History of bleeding diathesis or coagulopathy that precludes anticoagulation
22. Active gastrointestinal (GI) bleeding that would preclude anticoagulation
23. Known hypersensitivity or contraindication to nitinol, or sensitivity to contrast media which cannot be adequately pre-medicated
24. Any cardiac or peripheral interventional procedure performed within 30 days prior to enrollment in patients treated with bare-metal stent or drug-eluting stent (DES) with approved 1-month DAPT labeling or within 90 days prior to enrollment for subjects treated with DES without approved 1-month labeling.
25. Untreated clinically significant coronary artery disease requiring revascularization
26. Severe symptomatic carotid stenosis
27. Recent Stroke or TIA within 90 days of enrollment
28. Evidence of an acute myocardial infarction within 90 days prior to enrollment
29. Active endocarditis or active infection requiring antibiotic therapy
30. Implant of any Cardiac Resynchronization Therapy (CRT) or Cardiac Resynchronization Therapy with cardioverter-defibrillator (CRT-D) within 90 days of enrollment
31. End stage renal disease requiring chronic dialysis or creatinine clearance < 30 cc/min within 30 days of the Index Procedure
32. Severe Chronic Obstructive Pulmonary Disease (COPD) demonstrated by Forced Expiratory Volume (FEV1) < 750cc
33. Pregnancy, breastfeeding, or intent to become pregnant prior to completion of all protocol follow-up requirements
34. Currently participating in an investigational drug or another device study that has not yet reached its primary endpoint
35. Other medical, social, or psychological conditions that in the opinion of the Investigator precludes the subject from appropriate consent or adherence to the protocol required follow-up exams

*Medtronic Business Restricted*

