**Table 9-1: Schedule of Events Table**

	Screening & Baseline	Pre-Index Procedure	Index Procedure	Discharge	1 Month	3 Months	6 Months	12 Months	Every 6 Months through 5 Years
Medications	X	X		X	X	X	X	X	X
Heart Failure	X	X	X	X	X	X	X	X	X
1. If female and child-bearing age 2. mRS is required to be collected at screening and conducted at 30 and 90 days following any stroke or TIA event, as applicable 3. B-type Natriuretic Peptide (BNP) or NT-proBNP, along with Creatinine, CBC and Albumin required at follow-up visits 4. INR levels to be monitored and reported for all subjects receiving warfarin anticoagulation therapy 5. TTE with limited views is required within 7 days of the Index Procedure to assess cardiac status (i.e. cardiac index, LVEF, PA pressure and mitral regurgitation) 6. If clinically necessary, or at Investigator discretion, TEE is to be conducted in addition to TTE to further evaluate any potential clinically significant findings during the follow-up period 7. Right heart catheterization may be used to supplement TTE measurements, as applicable 8. Complete visualization of femoral veins and inferior vena cava up to and including the mitral annulus 9. Subjects declining the MDCT at time of follow-up or unable to have the assessment will not be considered a protocol deviation 10. Adverse events collected after the subject is enrolled in the study. 11. Quality of Life Questionnaires collected at baseline (Minnesota Living with Heart Failure Questionnaire, SF-12 and KCCQ) may be administered any time after the subject has been approved for enrollment									

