## 9.10 Discharge

Subjects will be cared for through discharge according to standard procedures for mitral valve replacement surgery.

Antithrombotic medication is recommended to be initiated in accordance with local practice and no earlier than Day 1 post-operatively. The recommended post-implant regimen for all subjects

is dual anticoagulation/antiplatelet therapy for a minimum of 6 months with a target INR of 2.5. Dual warfarin and aspirin (81mg) are recommended.

It is also recommended that deep vein thrombosis (DVT) prophylaxis be administered in accordance with local practice for any subject treated, until the INR reaches therapeutic level.

Prior to discharge (or within 14 days post procedure whichever comes first), the following standard exams and tests will be performed:

- Physical exam and review of adverse events and device deficiencies
- Heart Failure Management & Medications
- TTE (addition of TEE evaluation if deemed clinically necessary, or at Investigator discretion)
- 12-lead ECG
- Laboratory tests
  - Creatinine
  - Complete Blood Count
  - Albumin
  - B-type Natriuretic Peptide (BNP) or NT-proBNP
  - INR, if applicable (INR levels to be monitored and reported for all subjects receiving warfarin anticoagulation therapy)
- Multidetector Computed Tomography (MDCT)

Subjects declining the MDCT at time of follow-up or unable to have the assessment will not be considered a protocol deviation

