### 17.1.2 ACUTE KIDNEY INJURY

Acute Kidney Injury (AKI) will be defined and classified according to the Mitral Valve Academic Research Consortium (MVARC); Clinical Trial Design Principles and Endpoint Definitions for Transcatheter Mitral Valve Repair and Replacement: Part 2: Endpoint Definitions; JACC, 2015 (14).

Definition and Stages of Acute Kidney Injury	
Definition	Maximal changes in sCr from baseline to 7 days post-procedure
Stages	
Stage 1	Increase in sCr to 150%–199% (1.50–1.99x increase vs. baseline), increase of $\geq 0.3$ mg/dl ( $\geq 26.4$ mmol/l) within 48 h, or urine output $<0.5$ ml/kg/h for $\geq 6$ h but $<12$ h
Stage 2	Increase in sCr to 200%–299% (2.00–2.99x increase vs. baseline) or urine output $<0.5$ ml/kg/h for $\geq 12$ h but $<24$ h
Stage 3	Increase in sCr to $\geq 300\%$ ( $\geq 3.0$ x increase vs. baseline), sCr of $\geq 4.0$ mg/dl ( $\geq 354$ mmol/l) with an acute increase of $\geq 0.5$ mg/dl (44 mmol/l), urine output $<0.3$ ml/kg/h for $\geq 24$ h, or anuria for $\geq 12$ h; patients receiving renal replacement therapy are considered stage 3 irrespective of other criteria
Adapted with permission from Kappetein et al. Updated standardized endpoint definitions for transcatheter aortic valve implantation: The Valve Academic Research Consortium-2 consensus document. J Am Coll Cardiol 2012;60: 1438–54.	

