## 17.1.33 MYOCARDIAL INFARCTION

Myocardial infarction (MI) will be defined according to the Mitral Valve Academic Research Consortium (MVARC); Clinical Trial Design Principles and Endpoint Definitions for Transcatheter Mitral Valve Repair and Replacement: Part 2: Endpoint Definitions; JACC, 2015 (14).

Definition of MI After Transcatheter and Surgical Mitral Valve Replacement	
I. Periprocedural MI (<math>\leq 48</math> h after the index procedure)*†	
A.	In patients with normal baseline CK-MB (or cTn): The peak CK-MB measured within 48 h of the procedure rises to $\geq 10$ times the local laboratory ULN plus new ST-segment elevation or depression of $\geq 1$ mm in $\geq 2$ contiguous leads (measured 80 ms after the J-point), or to $\geq 5$ times ULN with new pathological Q waves in $\geq 2$ contiguous leads or new persistent LBBB, OR in the absence of CK-MB measurements and with a normal baseline cTn, a cTn (I or T) level measured within 48 h of the PCI rises to $\geq 70$ times the local laboratory ULN plus new ST-segment elevation or depression of $\geq 1$ mm in $\geq 2$ contiguous leads (measured 80 ms after the J-point), or $\geq 35$ times ULN with new pathological Q waves in $\geq 2$ contiguous leads or new persistent LBBB.
B.	In patients with elevated baseline CK-MB (or cTn): The CK-MB (or cTn) rises by an absolute increment greater than or equal to those levels recommended above from the most recent pre-procedure level plus, new ECG changes as described.
II. Spontaneous MI (<math>>48</math> h after the index procedure)‡	
Detection of rise and/or fall of cardiac biomarkers (preferably cTn) with at least 1 value above the 99th percentile URL (or ULN in the absence of URL) together with at least 1 of the following:	
A.	Symptoms of ischemia
B.	ECG changes indicative of new ischemia (new ST-segment or T-wave changes or new LBBB) or new pathological Q waves in $\geq 2$ contiguous leads
C.	Imaging evidence of a new loss of viable myocardium or new wall motion abnormality
III. MI associated with sudden, unexpected cardiac death‡	
Sudden cardiac death or cardiac arrest, often with symptoms suggestive of myocardial ischemia, and accompanied by presumably new ST-segment elevation or new LBBB and/or evidence of fresh thrombus by coronary angiography and/or at autopsy, but death occurs before blood samples could be obtained or at a time before the appearance of cardiac biomarkers in the blood	

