## Appendix A: Schedule of Visits and Procedures

Test / Evaluation	Baseline	Implant Procedure	Discharge	1, 3, 6M (± 2 wks)	12M (± 30 days)	Every 6M (± 30 days) through 5 yrs
Informed Consent	X					
Medical History	X					
Physical Exam (including NYHA Class)	X		X	X	X	X
6-minute walk test	X			X	X	X
Blood Tests: Chemistries (incl. creatinine), CBC, CK/CK-MB, Coagulation panel, plasma free hemoglobin	X	X	X	X	X	X
Pregnancy Test (blood or urine), if appropriate	X					
ECG (12 lead)	X	X	X	X	X	X
Coronary angiogram	X					
Transthoracic Echocardiography (TTE)	X		X 	X 	X 	X 
Transesophageal Echocardiography (TEE)	X	X	X 	X 	X 	X 
Cardiac Computed Tomography (CT)	X		X		X	
Hemodynamics		X				
Quality of Life (QOL) Survey	X				X	
Adverse Events	X	X	X	X	X	X

 TTE or TEE per physician discretion

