## **Appendix B: Participant Information and Consent Form**

## **Appendix C: Instructions for Use**

## Appendix D: Endpoint Definitions

Analysis of study results will include the following additional MVARC defined exploratory endpoints:

**Technical Success** (measures at exit from catheterization laboratory)

All of the following must be present:

- I. Absence of procedural mortality; and
- II. Successful access, delivery, and retrieval of the device delivery system; and
- III. Successful deployment and correct positioning of the first intended device; and
- IV. Freedom from emergency surgery or reintervention related to the device or access procedure

**Device Success** (measured at 30 days and at all later post-procedural intervals):

All of the following must be present:

- I. Absence of procedural mortality or stroke; and
- II. Proper placement and positioning of the device; and
- III. Freedom from unplanned surgical or interventional procedures related to the device or access procedure; and
- IV. Continued intended safety and performance of the device, including:
  - a. No evidence of structural or functional failure
  - b. No specific device-related technical failure issues and complications
  - c. Reduction of MR to either optimal or acceptable levels without significant mitral stenosis (i.e., post-procedure EROA is 1.5 cm^2 with a transmural gradient <5 mm Hg), and with no greater than mild (1+) paravalvular MR (and without associated hemolysis)

**Procedural Success** (measured at 30 days)

All of the following must be present:

- I. Device success (either optimal or acceptable), and
- II. Absence of major device or procedure related serious adverse event, including:
  - a. Death
  - b. Stroke
  - c. Life-threatening bleeding (MVARC scale)
  - d. Major vascular complications
  - e. Major cardiac structural complications
  - f. Stage 2 or 3 acute kidney injury (includes new dialysis)
  - g. Myocardial infarction or coronary ischemia requiring PCI or CABG
  - h. Severe hypotension, heart failure, or respiratory failure requiring intravenous pressors or invasive or mechanical heart failure treatments such as ultrafiltration or hemodynamic assist devices, including intra-aortic balloon pumps or left ventricular or biventricular assist devices, or prolonged intubation for 48 h
  - i. Any valve-related dysfunction, migration, thrombosis, or other complication requiring surgery or repeat intervention

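### Detection of periprocedural MI and creatinine-defined AKI in the EFS depends on tests its schedule does not require, so counts may be incomplete and may vary by site

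*Combined protocol and SAP*

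**What the plan says.** **MI.** EFS CIP 17.1.33 makes a periprocedural MI (up to 48 h) depend on an enzyme rise together with new ECG changes. For a subject with a normal baseline the criterion reads "The peak CK-MB measured within 48 h of the procedure rises to" at least 10 times the upper limit of normal with ST change, or at least 5 times with new Q waves or persistent LBBB. Where CK-MB is not measured, "a cTn (I or T) level measured within 48 h of the PCI rises to" at least 70 or 35 times the limit, with the same ECG findings. (That sentence names a PCI; the index procedure is presumably meant.) If the baseline enzyme is raised, the increment is judged against the most recent pre-procedure value.

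**AKI.** EFS CIP 17.1.2 uses "Maximal changes in sCr from baseline to 7 days post-procedure". Stages can also be met by urine output, and renal replacement therapy counts as stage 3 regardless of creatinine.

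**Schedule.** Table 9-1 places laboratory tests at screening, discharge and each follow-up visit, with none at the pre-index or index visit. Footnote 3 lists BNP or NT-proBNP, "along with Creatinine, CBC and Albumin required at follow-up visits". Sections 9.5.2, 9.10 and 9.11 give the same panel plus INR for subjects on warfarin. On the discharge tests, 9.10 says: "Prior to discharge (or within 14 days post procedure whichever comes first), the following standard exams and tests will be performed". The 12-lead ECG follows the same columns as the laboratory tests.

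**The concern.** The event definitions rest on measurements that the visit schedule does not require. For an event endpoint this gap is hard to see afterwards. A subject with no enzyme measured, or no creatinine near the peak, is simply counted as not having had the event. EFS CIP 13.1 promises the number of subjects with available data so that the effect of missing data can be judged, but an absent event record does not show up as missing.

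What is at stake is the main product of a descriptive study. The primary objective is the nature, severity and frequency of complications, and both MI and renal failure are listed risks in 10.1. Sites that test routinely will find more events than sites that do not, so a difference between sites could reflect testing practice rather than outcome.

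The Pilot CIP in the same file draws attention to the gap: its Appendix A schedules "Blood Tests: Chemistries (incl. creatinine), CBC, CK/CK-MB, Coagulation panel, plasma free hemoglobin" at baseline, implant, discharge and follow-up.

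**Working it through.** The plan has no figure to reproduce here. The EFS sample size is up to 45 and is stated not to be statistically derived. The check compares each definition with the schedule.

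**Step 1. Needed versus required** (EFS CIP 17.1.2, 17.1.33, Table 9-1, Table 9-2, 9.5.2, 9.10, 9.11)

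| Measurement | Definition needs | Schedule requires |
|---|---|---|
| CK-MB or troponin, baseline | One pre-procedure value | None |
| CK-MB or troponin, post-procedure | Peak within 48 h | None at any visit |
| 12-lead ECG | New changes accompanying the enzyme rise | Screening, then discharge or day 14 |
| Creatinine, baseline | One value, not further specified | Screening value; earlier clinical results accepted, no age limit stated |
| Creatinine, post-procedure | Maximum to day 7 | One, at discharge or by day 14 |

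The next scheduled draw is the 1-month visit: 30 ± 14 = day 16 to day 44.

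**Step 2. Counts.** Scheduled draws after the procedure and before the 1-month visit:
- CK-MB: 0
- troponin: 0
- creatinine: 1

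Creatinine draws guaranteed by day 7: 0, because the single draw may fall on days 8 to 14. If discharge is early, the draw may come before the peak. From scheduled tests alone, no subject can meet periprocedural criterion I.A or I.B. That follows from the schedule and is not an estimate of missed events.

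**Step 3. AKI illustration (assumed values).** Screening creatinine 1.2 mg/dL, day-3 peak 2.6, day-6 discharge value 1.4.
- Peak: 2.6 / 1.2 = 217%, stage 2 (200–299%).
- Discharge: 1.4 / 1.2 = 117%, and the rise of 0.2 is below 0.3 mg/dL, so no stage is met.

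The scheduled data show no event. The inpatient chart would show one if day 3 was tested.

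**Step 4. Scale.** One event is 1/45 = 2.2 percentage points. The event and capture rates below are assumptions, because the documents give neither. Capture is the fraction of true events that are recorded.
- Expected recorded events = 45 × true rate × capture.
- Chance of recording none = (1 − true rate × capture)^45.

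| True rate | Capture | Expected true | Expected recorded | Chance of recording none |
|---|---|---|---|---|
| 5% | 100% | 2.25 | 2.25 | 0.099 |
| 5% | 80% | 2.25 | 1.80 | 0.159 |
| 5% | 40% | 2.25 | 0.90 | 0.403 |
| 10% | 100% | 4.5 | 4.5 | 0.009 |
| 10% | 40% | 4.5 | 1.8 | 0.159 |
| 30% | 80% | 13.5 | 10.8 | <0.001 |
| 30% | 40% | 13.5 | 5.4 | 0.003 |

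A reported 0/45 has an exact two-sided 95% upper limit of 1 − 0.025^(1/45) = 7.9%. That limit holds only if all 45 subjects were assessed for the event.

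**The case against.** The strongest reply is that scheduled visits are not the only source of data. Under 9.10, inpatient care follows standard practice for mitral valve replacement surgery. Adverse events are collected from enrollment, and Table 11-1 counts abnormal laboratory findings among them. The sponsor may request source documents to support adjudication (11.5.2), and the CEC charter, which is not in the file, is to set the minimum data for each event (12.1). This stands in part. It shows that values may exist, but no frequency of inpatient testing is stated, an abnormal value is reportable only if it was drawn, and the CEC cannot adjudicate a test that was not done.

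Several stronger readings are tempting, and the documents do not support them:

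- **That the schedule contains no cardiac biomarker.** BNP or NT-proBNP is required at screening, discharge and follow-up. Only markers of myocardial necrosis are absent.
- **That both harms are under-counted.** The documents support a risk of incomplete counts, not a demonstrated shortfall. Urine output, dialysis, and MI types III and IV need no scheduled enzyme or creatinine.
- **That the primary endpoint is materially biased.** It counts related serious events. Silent enzyme rises and transient creatinine rises, the events most easily missed, are the least likely to be serious.
- **That procedural success is biased upward.** The list containing "Stage 2 or 3 acute kidney injury (includes new dialysis" is in Pilot CIP Appendix D and is repeated in SAP 7.9.3, and that SAP is for CIP-1403. The MI component there is worded together with coronary ischemia requiring PCI or CABG, within major related serious events. EFS CIP 17.1 gives no composite definition, so the link to the EFS is inferred.
- **That the Pilot schedule shows a necessary test was dropped.** The Pilot used transapical access and does not tie CK-MB to 48 h. Its sections 4.2 to 4.4 list no blood test at the procedure; only its Appendix A does.
- **That exclusion 31 ("creatinine clearance < 30 cc/min within 30 days of the Index Procedure") goes unchecked.** Section 9.7 requires all exclusion criteria to be reconfirmed before the procedure. The remaining gap is that Table 9-1 shows no laboratory test at that visit and no AKI baseline value is named.

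**Conclusion.** The mismatch is confirmed in the text. Finding an enzyme-defined periprocedural MI, or an AKI defined by creatinine alone, depends on unscheduled local testing. Counts may therefore be incomplete and may differ between sites for reasons unrelated to outcome. The most exposed events are silent MI and transient stage 1–2 AKI.

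The size of any under-count cannot be computed: neither the event rates nor the frequency of local testing is given, and Step 4 shows scale only. A reader might go on to conclude that the 30-day safety rate is biased down, but for the reasons above the effect on that endpoint is probably small. Any effect on EFS procedural success, an exploratory outcome with no pass criterion, rests on assuming that the Pilot's components apply.

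This rests on reading Table 9-1 with 9.5.2, 9.10 and 9.11 as the full set of required tests. The CEC charter and any EFS-specific analysis plan could narrow the gap but could not be consulted. It is a worthwhile low-cost improvement and does not put the study's design in question.

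**What to change.** 1. **Creatinine.** In 9.10 and the procedure/discharge CRF, record from the inpatient chart the highest creatinine from the procedure to day 7 or discharge, whichever is first. Record the last pre-procedure creatinine with its date and name it as the AKI baseline. The same entry documents the exclusion 31 re-check under 9.7. A peak after an early discharge would still be missed.
2. **Enzymes and ECG.** Record any CK-MB, troponin and 12-lead ECG obtained before the procedure and within 48 h after it, including whether each was done.
3. **Reporting.** Give MI and AKI rates together with the number of subjects who had the measurements needed to assess each event.
4. **Reconciliation.** The sponsor should reconcile 17.1.33 with Table 9-1. Scheduling CK-MB or troponin and an ECG within 48 h is one option, but it adds procedures, and whether to do so is for the sponsor to settle.

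The cost of items 1 to 3 is protocol wording, a few CRF fields and chart abstraction, which can also be done for subjects already treated. The downside is that reported AKI and MI rates may look slightly less favourable.

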# The Early Feasibility Study of the Intrepid™ TMVR Transseptal System Clinical Investigation Plan

Version 4.0

Page 93 of 102

Medtronic

## 17.1.34 NEUROLOGICAL EVENTS

Neurological Events will be defined and classified according to the Mitral Valve Academic Research Consortium (MVARC); Clinical Trial Design Principles and Endpoint Definitions for Transcatheter Mitral Valve Repair and Replacement: Part 2: Endpoint Definitions; JACC, 2015 (14).

Stroke and Transient Ischemic Attack: Diagnosis and Classification	
Diagnostic Criteria	

Acute episode of a focal or global neurological deficit with at least 1 of the following:
 

A. Change in the level of consciousness

B. Hemiplegia, hemiparesis, numbness, or sensory loss affecting 1 side of the body

C. Dysphasia or aphasia, hemianopia, amaurosis fugax, or other neurological signs or symptoms consistent with stroke

 
In addition, there is no other readily identifiable nonstroke cause for the clinical presentation (e.g., brain tumor, trauma, infection, hypoglycemia, peripheral lesion, pharmacological influences) as determined by or in conjunction with the designated neurologist*
	
The neurological event type classification	

Stroke: duration of a focal or global neurological deficit <math>\geq 24</math> h OR <math>< 24</math> h if available neuroimaging documents a new intracranial or subarachnoid hemorrhage (hemorrhagic stroke) or central nervous system infarction (ischemic stroke) OR the neurological deficit results in death
 
TIA: duration of a focal or global neurological deficit <math>< 24</math> h and neuroimaging does not demonstrate new hemorrhage or infarct
	
Confirmation of the diagnosis of stroke or TIA requires at least 1 of the following	

Neurologist or neurosurgical specialist, or Neuroimaging procedure (CT scan or brain MRI)
	
Stroke/TIA timing classification	

Periprocedural if it occurs within 30 days of the intervention, or if beyond 30 days in the patient not yet discharged. A periprocedural stroke/TIA may be further considered immediate if it occurs within 24 h of the procedure or within 24 h of awakening from general anesthesia if beyond 24 h.
 
Nonperiprocedural if it occurs beyond 30 days after the intervention and after the patient has been discharged.
	
Stroke/TIA etiology classification	

Ischemic: an acute episode of focal cerebral, spinal, or retinal dysfunction caused by infarction of the central nervous system tissue
 
Hemorrhagic: an acute episode of focal or global cerebral or spinal dysfunction caused by intraparenchymal, intraventricular, or subarachnoid hemorrhage
 
Undetermined: if there is insufficient information to allow categorization as ischemic or hemorrhagic
	

Medtronic Business Restricted

